8.3 Identity of the Investigational Products

8.3.1 Description of the Investigational Medicinal Products

MEN1611:

The drug product MEN1611 is a hypromellose capsule for oral administration. One capsule contains 20.07 mg of MEN1611 which corresponds to 16 mg MEN1611 free-base and the following inactive ingredients: Lactose monohydrate, croscarmellose sodium, hypromellose and magnesium stearate. All excipients used in the formulation are of compendial grade. The investigational medicinal product (IMP) is packed in Al/Al blisters.

Cetuximab:

Authorized market preparations will be used as combination medication. The market preparation is a solution for infusion. Dilution of the market preparation should follow the instructions reported in the respective summary of product characteristics (SmPC).

8.3.2 Packaging, Labelling and Storage

MEN1611:

The packaging and labelling of MEN1611 IMP is performed under the responsibility of the Department of Pharmaceutical Development of A. Menarini Research & Business Service GmbH (A.MRBS).

MEN1611 16 mg capsules will be packaged as described below:

- Primary packaging: The drug product MEN1611 will be primary packaged in Al/Al blisters.
- Secondary packaging: The IMP will be provided in treatment boxes (blister wallets). The Al/Al blisters will be permanently fixed in blister wallets.

Labelling: The IMP MEN1611 will be labelled in compliance with the current valid international and corresponding national requirements. The label will report instructions on how to administer and store the MEN1611 IMP.

Storage: At the study site, the MEN1611 IMP must be kept in a secure area inaccessible to unauthorised individuals. Furthermore, the Investigator will instruct the patient to keep MEN1611 boxes according to the storage conditions given on the label.

Distribution of MEN1611 treatment boxes to the study sites will be under responsibility of A.MRBS.

Cetuximab:

Cetuximab will be provided using authorized market preparations for EU and US sites.

EU Sites:

The primary packaging of the authorized market preparation will not be modified. Each vial will be labelled individually. The secondary packaging and labelling of cetuximab for EU sites is performed under the responsibility of the Department of Pharmaceutical Development of A.MRBS. As secondary packaging, the vials will be provided in labelled boxes. All labels will be in compliance with the valid international and corresponding national requirements. The labels will report instructions on how to administer and store cetuximab.

Storage: At the study site, cetuximab must be kept in a secure area inaccessible to unauthorised individuals in accordance to the storage conditions given on the label. Distribution of cetuximab to EU study sites will be under responsibility of A.MRBS.

US Sites:

Cetuximab for US study sites will be provided by the respective site's pharmacy.

8.3.3 Drug Accountability

MEN1611 (EU and US) and Cetuximab (EU)

Upon receipt of all study treatment, study site personnel or the designated pharmacist will open the shipment package, verify the contents as stated on the enclosed Delivery Note and confirm the receipt in the interactive web-response system (IWRS).

The IWRS will be used to record the study treatment delivery to study sites and patients, the inventory at the sites, including dates, quantities, expire dates and batch/serial number.

The Investigator will be responsible for documenting the dispensing of the study treatment to the patient by entering the unique medication number in the source documents and in the eCRF to allow drug accountability.

In addition, the sites will maintain paper drug accountability forms to document the dispensed and administered study treatment per patient. The peel-off labels will be pasted onto these paper drug accountability forms.

Patients will be instructed to return used or unused MEN1611 boxes at each visit to allow drug accountability for dispensed MEN1611.

Cetuximab (for US sites only)

The Investigator will be responsible for documenting the dispensing of the study treatment to the patient by entering the batch number in the source documents and in the eCRF to allow drug accountability. In addition, the sites will maintain paper drug accountability forms to document the dispensed and administered study treatment per patient.

8.3.4 Destruction of the Study Treatment

Throughout the study and at the end of the study, all remaining study treatment will be reconciled under the responsibility of the Investigator at the study site.

MEN1611 (EU and US)

No later than the Site Close-out Visit, the used and unused MEN1611 IMP boxes shall be returned to the Department of Pharmaceutical Development of A.MRBS for destruction, provided this is not in conflict with any national export legislation.

In case local destruction is required due to national legislations a certificate of destruction, indicating the batch number and the box number needs to be provided.

Cetuximab (for EU sites only)

Used and unused cetuximab boxes shall be destroyed locally. Any local destruction of cetuximab requires a certificate of destruction, indicating the batch number and the box number.

Cetuximab (for US sites only)

Used cetuximab boxes shall be destroyed locally.

8.4 Treatments

8.4.1 MEN1611

Step 1 (Dose-confirmation Phase): MEN1611 as oral capsules of 16 mg strength will be orally administered BID (approximately 12 hours apart) for a continuous 28-days cycle. The starting dose of MEN1611 will be 48 mg BID for a total daily dose of 96 mg. In case 48 mg BID in combination

with cetuximab will represent the toxic dose level for this combination, a lower dose level of 32 mg BID will be tested in cohort 2.

In this Phase, MEN1611 will be administered as below:

- Cohort 1: MEN1611 48 mg (3×16 mg) capsules BID over 28-days' cycle.
- Cohort 2: MEN1611 32 mg (2×16 mg) capsules BID over 28-days' cycle.

Step 2 (Cohort-expansion Phase): MEN1611 as oral capsules will be orally administered BID for a continuous 28-days' cycle at the RP2D as established in Step 1.

MEN1611 capsules should be taken with a glass of water in fasting condition, i.e. at least 2 hours after a meal and at least 1 hour before the next meal. Patient should take capsules at approximately the same time each day. At Visit 2, Visit 3 and Visit 4 of Cycle 1, and at each following visits, MEN1611 will be administered at site using the new boxes dispensed at each visit.

8.4.2 Cetuximab

In both Step 1 and Step 2, cetuximab will be administered IV weekly on Day 1, 8, 15 and 22 of every 28-day cycle according to institutional standards.

[figure not shown]
The initial cetuximab dose is 400 mg/m^2 administered as a 120 minutes infusion on Day 1 of Cycle 1, followed by a weekly 250 mg/m^2 dose administered as a 60-minute IV infusion. Premedication with a H1 receptor antagonist (e.g. d-chlorpheniramine or diphenhydramine) and a corticosteroid is required prior to cetuximab administration (see Section 8.4.8). Management of infusion reactions due to cetuximab are to be managed according to Section 8.4.5.

[figure not shown]
MEN1611 will be given in combination with weekly IV infusion of cetuximab until objective disease progression is documented or another criterion for discontinuation is met. If cetuximab needs to be discontinued due to toxicity, continuation with MEN1611 as monotherapy should be considered and discussed with the Sponsor.

[figure not shown]
8.4.3 Treatment Compliance

[figure not shown]
Patients will be asked to complete a paper patient diary for the duration of their treatment with MEN1611 to record the study treatment compliance (see Section 10.1.3).

[figure not shown]
8.4.4 Management of Toxicities due to MEN1611 and Dosage Modification

[figure not shown]

8.4.5 Management of Infusion-Related Reactions due to Cetuximab

One of the main undesirable effects of cetuximab are infusion-related reactions, which occur with mild to moderate symptoms in more than 10% of patients and with severe symptoms in more than 1% of patients.

Prophylaxis of Infusion-Related Reactions:

At least 1 hour prior to the first infusion of cetuximab, the patient must receive a premedication consisting of a corticosteroid and a H1 receptor antagonist.

This premedication is strongly recommended prior to all subsequent infusions.

As dexamethasone and prednisone are known to be inducers of isozyme CYP3A4, its administration during the study is allowed only prior to cetuximab infusions. In case the patient was receiving dexamethasone/prednisone before the study, the treatment should be stopped within a period corresponding to five times the half-life of the drug prior to the first MEN1611 administration (see Section 8.4.8).

Cetuximab must be administered under the supervision of a physician experienced in the use of antineoplastic medicinal products. The infusion rate should be consistent with the local label but should not exceed 10 mg/min. Close monitoring is required during the infusion and for at least one hour after end of the infusion. If an infusion reaction occurs while cetuximab is being administered, the infusion should be stopped immediately, and the patients should be closely monitored and treated in line with institutional standards. Availability of resuscitation equipment must be ensured. Symptoms may occur during the first infusion and for up to several hours afterwards or with subsequent infusions. It is recommended to inform patients of the possibility of such a late onset and inform them to contact the investigator if symptoms or signs of an infusion-related reaction occur.

Occurrence of a severe infusion-related reaction requires immediate and permanent discontinuation of cetuximab therapy and may necessitate emergency treatment.

If during the first infusion, an infusion-related reaction occurs within the first 15 minutes, the infusion should be stopped. If an infusion-related reaction develops later during the infusion or at a subsequent infusion further management will depend on its severity:

Table 8-5 Management of Infusion-Related Reactions due to Cetuximab

CTCAE v5.0	Action
Grade 1: Mild transient reaction; infusion interruption not indicated; intervention not indicated.	Decrease cetuximab infusion rate by 50% and monitor closely for any worsening. All subsequent infusions must also be administered at the reduced rate.
Grade 2: Therapy or infusion interruption indicated but responds promptly to symptomatic treatment (e.g. antihistamines, non-steroidal anti-inflammatory drugs [NSAIDs], narcotics, IV fluids); prophylactic medications indicated for <=24 hrs.	Stop cetuximab infusion. Administer symptomatic treatment as medically indicated. Restart and complete the infusion at the discretion of the investigator. The infusion must be resumed at reduced rate (once resolved or decreased to Grade 1). Additional premedications such as antihistamines or low-dose systemic corticosteroids may be administered when the infusion is restarted and monitored closely for any worsening. All subsequent infusions must also be administered at the reduced rate.
Grade 3: Prolonged (e.g. not rapidly responsive to symptomatic medication and/or brief interruption of infusion); recurrence of symptoms following initial improvement; hospitalisation indicated for clinical sequelae.	Stop infusion immediately, treat symptoms vigorously (e.g. administer epinephrine, bronchodilators, antihistamines, glucocorticoids, intravenous fluids, vasopressor agents, oxygen etc., as medical indicated). Permanently discontinue cetuximab.
Grade 4: Life-threatening consequences; urgent intervention indicated.	

Once a cetuximab infusion rate has been decreased due to an infusion reaction, it will be administered at the reduced rate for all subsequent infusions. Any rechallenge with cetuximab following an infusion reaction should be discussed with the Sponsor.

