2 PROTOCOL SYNOPSIS

Clinical Study Protocol Number	MEN1611-02
Title	Open-label, Multicentre, Phase Ib/II Study of MEN1611, a PI3K Inhibitor, and Cetuximab in Patients with PIK3CA Mutated Metastatic Colorectal Cancer Failing Irinotecan, Oxaliplatin, 5-FU and Anti-EGFR Containing Regimens
Acronym	C-PRECISE-01
Phase	Ib/II
Indication	Phosphatidylinositol 3-kinase, catalytic, alpha polypeptide gene (PIK3CA) mutated, N-K-RAS and BRAF wild type, metastatic colorectal cancer, in patients failing irinotecan, oxaliplatin, 5-FU and anti- epidermal growth factor receptor (EGFR) containing regimens.
Number of Sites and Countries	Approx. 29 sites in Europe and US.
Investigational Medicinal Product, Treatment Regimen (including route of administration)	
MEN1611, oral capsule: 16 mg capsules to be administered twice daily (BID) for a continuous 28-day cycle. Patients will receive MEN1611 either 48 mg or 32 mg BID (as 3 or 2 capsules, respectively), for a total daily dose of 96 mg or 64 mg, respectively. MEN1611 should be taken with a glass of water in fasting condition, i.e. at least 2 hours after the patient's meal and at least 1 hour before the next meal. Patients should take capsules at approximately the same time each day.
 
Cetuximab, solution for infusion: A loading intravenous (IV) dose of 400 mg/m² of cetuximab is administered as a 120 minutes infusion on Day 1 of Cycle 1, followed by weekly IV infusion (60 minutes) of 250 mg/m² maintenance doses starting from Day 8 of Cycle 1. Premedication with a corticosteroid and a histamine-1 (H1) receptor antagonist (e.g. d-chlorpheniramine or diphenhydramine) is required prior to cetuximab administration. Infusion reactions due to cetuximab are to be managed according to Section 8.4.5.

	MEN1611 will be given in combination with weekly IV infusion of cetuximab until objective disease progression is documented or another criterion for discontinuation is met. If cetuximab needs to be discontinued due to toxicity, patients may stay on study to receive MEN1611 as monotherapy.
Design	
This is an open-label, dose-confirmation and cohort expansion, multicentre, Phase Ib/II study.
 
Step 1 (Confirmation of Dose for Cohort Expansion): [REDACTED]
 
[REDACTED]
 
Step 2 (Cohort Expansion Phase): [REDACTED]
 
[REDACTED]
 
[REDACTED]
 
[REDACTED]
 
[REDACTED]
 
[REDACTED]

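### Protocol Section 8.4.5 gives two incompatible instructions for a Grade 1 cetuximab infusion reaction that occurs outside the first 15 minutes of the first infusion

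*Protocol*

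**What the plan says.** Section 8.4.5 contains three instructions on what to do when a reaction occurs.

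- **General sentence**, in the paragraph on supervision and monitoring: "If an infusion reaction occurs while cetuximab is being administered, the infusion should be stopped immediately". It names no grade, no time window and no particular infusion. It leaves treatment to institutional standards and gives no restart rule.
- **15-minute rule**: "If during the first infusion, an infusion-related reaction occurs within the first 15 minutes, the infusion should be stopped".
- **Lead-in to Table 8-5**: "If an infusion-related reaction develops later during the infusion or at a subsequent infusion further management will depend on its severity".

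Table 8-5 then sets actions by CTCAE v5.0 grade. The first row is defined as "Grade 1: Mild transient reaction; infusion interruption not indicated; intervention not indicated". Its action is "Decrease cetuximab infusion rate by 50% and monitor closely for any worsening", with the reduced rate kept for all subsequent infusions. The Grade 2 action begins "Stop cetuximab infusion. Administer symptomatic treatment as medically indicated" and allows the infusion to be restarted and completed at a reduced rate, at the investigator's discretion. The higher grades call for an immediate stop and permanent discontinuation of cetuximab.

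The synopsis adds no rule of its own: "Infusion reactions due to cetuximab are to be managed according to Section 8.4.5". Protocol Section 8.4.2 and SAP Section 5.1 make the same cross-reference.

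**The concern.** Staff facing a mild reaction at, say, the third weekly infusion find one sentence telling them to stop and a table telling them to carry on at half the rate. About 29 sites would each have to settle this for themselves.

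For the analysis, what is at stake is consistent safety reporting. TEAE severity by CTCAE grade is a secondary endpoint (Protocol Section 8.5.5.2, SAP Section 5.4.2). The grade definitions printed in Table 8-5 turn on whether interruption is called for, so a protocol sentence that requires a stop could lead one site to record Grade 2 where another records Grade 1. The SAP also plans a table of TEAEs leading to drug interruption (Section 11.5.3, Table 2.3.3.1). The same event might appear there from one site and not from another.

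**Working it through.** No formula decides the main point. The check is to apply each instruction to each situation.

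| Situation | General sentence | 15-minute rule | Table 8-5 | Compatible? |
|---|---|---|---|---|
| First infusion, first 15 minutes | Stop | Stop | Not invoked by its lead-in | Yes |
| Later in the first infusion, or any subsequent infusion: Grade 1 | Stop | Does not apply | Continue at half rate, monitor, keep the lower rate | **No** |
| Same timing: Grade 2 | Stop | Does not apply | Stop; may restart at a reduced rate | Yes, on stopping |
| Same timing: Grade 3 or 4 | Stop | Does not apply | Stop and discontinue permanently | Yes, on stopping |

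(In the text available, the Grade 4 action cell is empty. It is read here as shared with Grade 3, in line with the sentence in 8.4.5 on severe reactions.)

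One row fails. The next question is whether a stop-first, then-manage-by-grade reading rescues it.

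1. The Grade 1 row has neither a stop nor a restart. The Grade 2 row has both. If every infusion had already been stopped, the Grade 1 row would need a restart and the Grade 2 row would not need a stop.
2. The Grade 1 definition itself says that interruption is not called for.
3. A universal stop would make the separate 15-minute rule redundant.

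The reading does not fit the text, and the synopsis, Section 8.4.2 and the SAP only point back to 8.4.5, so nothing elsewhere breaks the tie.

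**Number affected.** The only incidence figures are mild to moderate reactions in more than 10% of patients and severe reactions in more than 1% (Section 8.4.5). Let N be the patients treated, p the mild-to-moderate rate, and f the share of those reactions that are Grade 1 and outside the 15-minute window. The affected count is N × p × f. The documents do not give f. As an illustration, take N = 40 (the efficacy-evaluable target, not the number treated) and p at its stated floor of 10%:

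- f = 0: 40 × 0.10 × 0 = 0 patients
- f = 1: 40 × 0.10 × 1 = 4 patients

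Because p is stated only as a lower bound, 4 is not a ceiling. The count is unknown.

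**Dose delivered.** Halving the rate changes duration, not dose. A 250 mg/m² infusion planned over 60 minutes runs at 250/60 = 4.17 mg/m² per minute. At half that rate it takes 250/2.083 = 120 minutes and delivers the same 250 mg/m². Dose is lost only if a site stops and does not restart. To see how large such a loss would have to be to matter for DLT evaluability, assume that the 75% cetuximab requirement refers to the planned Cycle 1 total and that the three later doses are given in full:

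- Planned total: 400 + 3 × 250 = 1150 mg/m²
- 75% of that: 862.5 mg/m²
- Needed from the loading infusion: 862.5 − 750 = 112.5 mg/m², or 112.5/400 = 28%, reached after about 0.28 × 120 = 34 minutes at a constant rate

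So a patient without a DLT would lose evaluability only if the loading infusion were abandoned before about 34 minutes. Nothing in the documents indicates that this would happen for a mild reaction.

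**The case against.** The strongest reply is that the general sentence is a precaution in a supervision paragraph, and that a specific graded table normally governs over a general statement. The lead-in speaks of further management, which can be taken as the step after an initial stop. Section 8.4.5 also already leaves treatment to institutional standards and the infusion rate to the local label, so some variation between sites is built in. This has weight: many sites may simply follow the table, so divergence is a risk and not an established fact. It does not remove the contradiction, because the Grade 1 row cannot be read as following a stop.

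Three stronger readings are tempting, and the documents do not support them.

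- *That at least 4 of 40 patients meet the conflict.* The 10% figure pools mild and moderate reactions, and Grade 2 does not conflict. It is also a general cetuximab figure. Patients here must have had a partial response or stable disease on a prior anti-EGFR regimen and must have no cetuximab hypersensitivity, so the figure need not carry over.
- *That stopping automatically raises the grade.* The definitions ask whether interruption is indicated, not whether it took place, and Grade 2 also describes prompt response to symptomatic treatment. Misgrading is possible but does not follow.
- *That cetuximab exposure is reduced.* A slower infusion delivers the same dose, and no route to dose loss at Grade 1 is shown beyond a stop without restart.

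**Conclusion.** The point stands as an internal inconsistency in Section 8.4.5, limited to Grade 1 reactions that arise after the first 15 minutes of the first infusion or at any subsequent infusion. For those events the section orders both a stop and a continuation at half rate. Reactions inside the 15-minute window and reactions of Grade 2 or above are not in conflict on whether to stop.

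The possible consequences are inconsistent bedside management, inconsistent grading of a mild event, and uneven counting in the drug-interruption table. The last assumes that a pause within an infusion is recorded as a drug interruption, which the SAP does not specify. No effect on the Step 2 primary endpoint, locally assessed response rate, is shown. The SAP plans no dedicated infusion-reaction analysis, so the effect on reporting is confined to the general adverse event tables. The correction is worth making because it concerns a safety instruction used at every weekly infusion.

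**What to change.** The sponsor should reconcile the general stop sentence, the 15-minute rule and Table 8-5, so that Section 8.4.5 gives one set of actions by grade and timing. Which action applies to a Grade 1 reaction is a clinical decision for the sponsor, and this review takes no position on it. Because the synopsis, Section 8.4.2 and SAP Section 5.1 only refer to 8.4.5, they need no separate change on this point. The cost is protocol wording, with no change to sample size, endpoints or analysis.

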8.4.6 Management of Skin Toxicities due to Cetuximab

The main undesirable effects of cetuximab are skin reactions, which occur in more than 80% of patients. Clinical judgement and experience of the investigator should guide the management plan of each patient.

General educational and prophylactic measures: Washing with lukewarm water, use shower oil or soap with neutral pH, use only perfume free cream, sunlight protection factor (SPF)≥25, wearing sun-protective clothes, application of topical agents (e. g. sunscreen, vitK1, emollient creams, topical steroids) in some areas such as face, scalp, neck, upper chest and upper back. Prophylactic recommendations should follow the clinical practice and local regulations for cetuximab administration.

In symptomatic patients who develop skin toxicity it is recommended to receive antihistamine for pruritic lesions, silver nitrate or zinc oxide cream for fissuring and emollients for desquamation.

Table 8-6 Management of Skin Rash (39)

Severity/Grade of Skin Rash CTCAE v5.0	Symptoms	Cetuximab Dose Modifications	Topical Treatment	Systemic Treatment	Intervention
Grade 1 (mild)	Papules and/or pustules covering <10% of BSA, which may or may not be associated with symptoms of pruritus or tenderness	No	-Topical antibiotics, BID (e.g. Metronidazole cream) and/or -Topical corticosteroid -Vitamin K1 cream	Possibly oral antibiotics (Doxycycline, Minocycline)	General educational and prophylactic measures
Grade 2 (moderate)	Papules and/or pustules covering 10 - 30% BSA, which may or may not be associated with symptoms of pruritus or tenderness; associated with	No	Topical corticosteroids, (e.g. mometasone)	Oral antibiotics (Doxycycline 100 mg BID, Minocycline 50 TO 100 BID)	General educational and prophylactic measures

Severity/Grade of Skin Rash CTCAE v5.0	Symptoms	Cetuximab Dose Modifications	Topical Treatment	Systemic Treatment	Intervention
	psychosocial impact; limiting instrumental ADL		Topical antibiotics (clindamycin)		
Grade 3 (severe)	Papules and/or pustules covering >30% BSA with moderate or severe symptoms; limiting self-care ADL; associated with local superinfection with oral antibiotics indicated.	Omit dose until resolved to \leq G2. First occurrence: If there is an improvement continue at 100% dose. Second and third occurrences of severe skin reactions, cetuximab therapy must again be interrupted. Treatment may only be resumed at a lower dose level (200 mg/m ² after the second occurrence and 150 mg/m ² after the third occurrence), if the reaction has resolved to Grade 2. Fourth occurrence or not resolved to Grade 2 during interruption of treatment, permanent discontinuation of cetuximab treatment is required.		Oral antibiotics (minocycline, doxycycline). Systemic Corticosteroids PO (methylprednisolone, prednisone) [*] according to investigator judgement. In highly symptomatic/non responsive patients: Isotretionin 0.3-05 mg/Kg PO; Antihistamines im/iv (clorfenamine); Antibiotics (amoxicillin/ac. Clav).	In addition to the interventions recommended for Grade 2 rash Consultation of dermatologist.

Severity/Grade of Skin Rash CTCAE v5.0	Symptoms	Cetuximab Dose Modifications	Topical Treatment	Systemic Treatment	Intervention
Grade 4 (potentially life-threatening)	Life-threatening consequences; Papules and/or pustules covering any % BSA, which may or may not be associated with symptoms of pruritus or tenderness and are associated with extensive superinfection with IV antibiotics indicated; life-threatening consequences.	Stop infusion immediately, contraindicate further use of cetuximab.		Isotretionin (Corticosteroids IV (methylprednisolone, dexamethasone) [*] Antihistamines IV (clorfenamine) Antibiotics IV (amoxicillin/ac. Clav) Hospitalisation.	Consultation of dermatologist.

If a patient experiences Grade 3 skin toxicity, cetuximab therapy may be deferred, without changing the dose level. If the toxicity resolves to Grade 2 or less by the following treatment period, the treatment may resume. With the second or third recurrences of Grade 3 skin toxicity, cetuximab therapy may again be deferred with concomitant dose reduction to 200 mg/m² and 150 mg/m², respectively. Cetuximab dose reductions are permanent. Patients should discontinue cetuximab if not resolved to Grade 2 or a fourth occurrence of Grade 3 skin toxicity occurs despite an appropriate dose reduction.

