5.7 Protocol/Protocol Modifications

The protocol must be read thoroughly by everyone, the information therein, concerns and the instructions must be exactly followed.

Changes in the study protocol will require a protocol amendment. Such amendments will be agreed upon and approved in writing by all signatories of the protocol. If amendments are substantial, i.e. they are likely to have an impact on the safety of the patients, or to change the interpretation of the scientific documents on which the trial is based or the scientific validity of the study results, significantly alter the nature of the management or conduct of the study, or impair the quality or safety of the investigational drugs, or if they are otherwise significant, the IRB/IECs and the CAs in the participating countries have to approve these amendments before implementation.

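### Protocol 8.4.6: the paragraph below Table 8-6 ties the cetuximab dose reductions to recurrences of Grade 3 skin toxicity, while the table ties them to occurrences

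*Protocol*

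**What the plan says.** Protocol 8.4.6 sets out what to do with cetuximab after Grade 3 skin toxicity in two places.

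**Table 8-6, Grade 3 row.** The dose is omitted until the reaction is Grade 2 or better. After a first occurrence that improves, treatment continues at 100% of the dose. For later episodes: "Second and third occurrences of severe skin reactions, cetuximab therapy must again be interrupted". The next sentence begins "Treatment may only be resumed at a lower dose level" and names 200 mg/m² after the second occurrence and 150 mg/m² after the third, provided the reaction has resolved to Grade 2. The end point is: "Fourth occurrence or not resolved to Grade 2 during interruption of treatment, permanent discontinuation of cetuximab treatment is required".

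**Paragraph below the table.** It opens: "If a patient experiences Grade 3 skin toxicity, cetuximab therapy may be deferred, without changing the dose level". Treatment may resume if the toxicity is Grade 2 or less by the following treatment period. It continues: "With the second or third recurrences of Grade 3 skin toxicity, cetuximab therapy may again be deferred with concomitant dose reduction to" 200 and 150 mg/m², respectively. It adds "Cetuximab dose reductions are permanent", which the table does not say. It closes: "Patients should discontinue cetuximab if not resolved to Grade 2 or a fourth occurrence of Grade 3 skin toxicity occurs" despite an appropriate dose reduction.

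The starting point for both is the weekly maintenance dose of 250 mg/m² (Protocol 8.4.2). Protocol 5.7 says of the protocol as a whole that "the instructions must be exactly followed".

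**The concern.** The two statements use different counting words for the same dose steps. The table counts occurrences throughout. The paragraph counts recurrences for the two reductions and then goes back to occurrences for the stop. The first recurrence of an event is its second occurrence, so the two counts differ by one.

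This is an operative dosing rule for a severe toxicity. Sites have to read the paragraph as well as the table, because only the paragraph says that reductions are permanent. Nothing in 8.4.6 or elsewhere says which text governs if they differ. The opening of 8.4.6 leaves each patient's management plan to the investigator's judgement and experience, but that does not choose between two dose schedules. At stake is whether a patient with a third Grade 3 episode resumes cetuximab at the intended dose.

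There is a secondary difference in strength. The table omits the dose, requires interruption and requires the final stop. The paragraph says that therapy *may* be deferred, at the first episode and again later, and that patients *should* discontinue.

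**Working it through.** No sample size, power or error rate is involved. The check sets the two rules side by side, episode by episode.

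**Inputs.** Maintenance dose 250 mg/m² (Protocol 8.4.2). Dose steps 200 and 150 mg/m² and the stop rule, from Table 8-6 and from the paragraph below it (Protocol 8.4.6).

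**Conversion.** Recurrence number n = occurrence number n + 1. So the second recurrence is the third occurrence, and the third recurrence is the fourth occurrence.

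| Grade 3 episode | Table 8-6 | Paragraph, read literally | Paragraph, with *recurrences* read as *occurrences* |
|---|---|---|---|
| 1 | 100% (250 mg/m²) | dose level unchanged | dose level unchanged |
| 2 | 200 mg/m² | no step stated (first recurrence) | 200 mg/m² |
| 3 | 150 mg/m² | 200 mg/m² (second recurrence) | 150 mg/m² |
| 4 | stop, required | 150 mg/m² (third recurrence), but also stop under its last sentence | stop, worded as *should* |

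**What the comparison shows.**

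1. Episode 1: the doses agree.
2. Episode 2: the literal paragraph is silent. Its reductions begin at the second recurrence, so it gives no step for the first.
3. Episode 3: the stated doses differ, 200 against 150 mg/m². The difference is 200 − 150 = 50 mg/m² per infusion, and 200 / 150 = 1.33, or one third more than the table.
4. Episode 4: the literal paragraph clashes with itself, because the 150 mg/m² step falls on the episode at which it calls for discontinuation.
5. With *occurrences* in place of *recurrences*, the paragraph matches the table on dose at every episode.

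**A check on point 3.** If a site has already used the table at episode 2, the patient is at 200 mg/m². The literal paragraph at episode 3 would then move the dose from 200 to 200 mg/m², a reduction of 0. This again suggests that the literal count was not intended.

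**Strength of wording.** Table: omit, must interrupt, stop required. Paragraph: may defer, may again defer, should discontinue. A site that interrupts because the table says *must* also complies with *may*. A site that stops because the table requires it also complies with *should*. On the verbs, following the table satisfies both texts.

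**The case against.** The best defence is that only one reading is coherent. The paragraph runs in order: a Grade 3 event with no dose change, then second and third with 200 and 150 mg/m², then fourth with a stop. That is the table's sequence, and the table stands directly above it. The literal reading leaves one episode without a step and gives another both a dose and a stop. This stands. It is why the word should be called a slip and not a rival dosing scheme. It does not make the word correct, and no statement of precedence resolves it.

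On the verbs, a reader might infer that the two texts contradict each other, or that the paragraph makes interruption and the final stop optional. The documents do not support that. Following the table satisfies both. The paragraph's condition for resuming implies that treatment is held until the toxicity improves. Protocol 8.4.5 also uses *should* for plainly expected safety actions, such as stopping an infusion when a reaction occurs. What remains is a weaker wording of the same instruction.

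A reader might also infer that a site using the paragraph would keep 250 mg/m² at the second episode, 25% above the table's 200. That supplies a dose the literal text does not give: it extends the unchanged-dose sentence to an episode for which the paragraph states no step.

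Other safeguards limit the consequences. A dermatology visit is required at Grade 3 or higher (Protocol 8.5.1). Study treatment is withdrawn when toxicity related to study drug delays it by more than 21 days (Protocol 8.2.3.2). The DSC meets at least every 3 months in Step 2, with the need for dose reductions monitored in all patients (Protocol 8.7). None of these settles the wording.

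**Conclusion.** The inconsistency is real and small. The paragraph below Table 8-6 uses the wrong counting word for the two cetuximab reductions. Read literally, it departs from the table at the second and third episodes and from its own stop rule at the fourth. The intended scheme is clear from the table: unchanged dose, 200 mg/m², 150 mg/m², stop.

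The only difference between two stated doses is 200 against 150 mg/m² at the third episode. It arises only if a site takes the word literally and uses the paragraph without the table. The documents do not say how often Grade 3 skin episodes recur in a patient, so the number who could be affected is unknown.

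The softer verbs are worth aligning but are not a second contradiction. A reader might go further and expect consequences for the RP2D, DLT evaluability or the efficacy results. Nothing in the protocol or SAP shows such an effect, and none is claimed. This is a minor dosing-safety correction.

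**What to change.** In the paragraph below Table 8-6, replace *recurrences* with *occurrences*. Change the two instances of *may* that govern deferral to *must*, and change *should* to *must* for the final discontinuation. The paragraph then gives unchanged dose, 200 mg/m², 150 mg/m², stop, and agrees with the table in dose and strength at every episode.

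Keep the paragraph. Deleting it would remove the only statement that dose reductions are permanent. It would also remove wording that covers Grade 3 skin toxicity in general, whereas Table 8-6 is titled and graded for rash.

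The cost is one word and three verbs in the next amendment, with a short note to sites.
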